## Background & Significance

To reduce the rising cost of cardiac operations, researchers have studied early extubation as a means to shorten ICU length of stay, and favorably influence patients' health outcomes. In the process, various nursing ICU protocols have been developed to facilitate the expedient tracheal extubation of patients, taking into account hemodynamic status, mediastinal drainage, urine output, patient temperature (rewarming from induced hypothermia), and other factors.

Hypothermia on admission to the ICU following CPB is common. Cooling and rewarming during CPB and takes considerable time and contributes to the post-procedural coagulopathy and physiologic perturbations.

Rewarming in the postoperative period after hypothermic CPB is often associated with hemodynamic and ventilatory instability. Temperature changes, PaCO2 values, and mechanical ventilation were observed for the first 12 hours in the ICU in 73 patients who had undergone cardiac surgery with hypothermic CPB. Mean rectal temperature increased from 34.7 to 38.3 degrees C over the first 8 hr after admission to the ICU. The temperature curve was sigmoid rather than linear, and the most rapid rate of temperature increase occurred 2-4 hours after admission. During rewarming, the most common abnormality of PaCO2 on mechanical ventilation was acute respiratory acidosis (PaCO2 greater than 45 mmHg, pH less than 7.35), which occurred in 42% of patients.

After disconnecting from CPB the body is allowed to self-equilibrate. The normal vasoconstriction response is impaired by the administered anaesthesia. Hence, heat distribution takes place from the warm core to the colder periphery. This causes an afterdrop: a decrease in the temperature of the core organs. After-drop may contribute to post-operative complications of hypothermia such as shivering, coagulopathy, increased myocardial stress, increased wound infections, metabolic acidosis, delayed extubation and prolonged ICU length of stay.

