## **Design & Procedures**

Hypothermia ( $\leq 35$  °C) after cardiac surgery using CPB is not uncommon. To avoid complications associated with hypothermia, and due to absence of shivering when patient is sedated, and harmful effects of shivering when patient is awake, clinicians resort to active warming devices. Forced air warming devices are the most commonly utilized, but occasionally heated humidified breathing circuits are used as well. We plan to use both warming devices on study patients, and compare them with a historical cohort that has used forced air warming device only.

On admission to CTICU, if temperature  $\leq 35$  °C, we will attempt to recruit the patient. Patients are intubated and sedated on admission to the CTICU after cardiac surgery, so informed consent will be obtained from the patient's next of kin or power of attorney. After consent is obtained, the clinical provider will ask the patient's nurse to place a lower body forced air warming device and set to 38 °C, and ask the respiratory therapist to set up and connect a heated humidified breathing circuit.

Admission temperature and other vital signs will be recorded per CTICU standards. Other patient management decisions (ie medication changes, laboratory assessments...etc) per direction of ICU providers. Core temperature and location (esophageal, nasopharyngeal, bladder, rectal, blood) will be recorded every 15-30 minutes until normothermia reached (36.5 °C), then record per CTICU standard. Record active warming methods in nursing flow sheets (i.e. Forced air warming blanket and heated humidified breathing circuit). Record other vital signs, medications, extubation time, hourly chest tube output, and patient data per unit policy. Alert Respiratory therapy once normothermia (36.5 °C) has been achieved for discontinuation of HHBC.

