#### **Consent Process**

Typically, patients remain intubated and sedated until hypothermia resolves. Patients will not be able to consent for themselves for this study. Informed consent will be obtained from next of kin / power of attorney.

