### **Data Analysis & Statistical Considerations**

Descriptive statistics will be used to evaluate patient demographics and clinical characteristics. Descriptive statistics will be summarized as mean  $\pm$  (SD) or median (interquartile range) for continuous variables and group frequencies (%) for dichotomous or categorical variables.

As all patients are expected to achieve normothermia within the study period, the primary outcome of time to normothermia will be analyzed as a numeric outcome variable. Following validation of distributional assumptions we will compare the time to normothermia between the two groups via t-test or Wilcoxon rank sum test as appropriate. It is expected that the patients will reach normothermia between 45 minutes and 6 hours after admission to the ICU.

By using a 2:1 matching ratio and a moderate level of variability (SD=1.3 hours) a study of 14 prospectively enrolled patients and 28 retrospectively matched patients would attain 82% power to detect a 1.25 hour difference between time to normothermia in the two groups at alpha level 0.05.

Secondary numeric outcomes such as time to extubation, time to normal PH, and coagulopathy lab values will be analyzed by t-test or Wilcoxon rank sum test as appropriate. Differences in categorical outcomes between treatment groups such as shivering will be analyzed via chi-square or fisher exact tests. As the patients will be matched on key confounders no further adjustment is expected to be necessary, so the moderate sample size should not limit the primary analysis. Potential subgroup analysis may be conducted in an exploratory analysis to determine if the treatment effect of ANAPOD warming is different by procedure type or patient/surgical characteristics.

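### The plan rests an unadjusted comparison with historical controls on matching, but the matching list does not name bypass duration, age, sex or surgical urgency, so confounding by these is uncontrolled

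*Combined protocol and SAP*

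**What the plan says.** The controls are not randomised. Under Design & Procedures, investigators will treat study patients with both warming methods and "compare them with a historical cohort that has used forced air warming device only".

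The matching criteria stand in the retrospective part, under Exclusion Criteria. Controls are hypothermic patients after bypass surgery who had forced air alone. The items then listed are temperature at the time the heated circuit is applied, type of surgery, BMI and deep hypothermic arrest. Bypass duration, age, sex and urgency are not named as matching items anywhere. Age appears only as an eligibility range of 18 to 85, stated for the prospective patients, and both sexes may enter.

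Data Analysis & Statistical Considerations specifies a t-test or Wilcoxon rank sum test for time to normothermia and for the numeric secondary outcomes. Its reason for stopping there is: "As the patients will be matched on key confounders no further adjustment is expected to be necessary". The same sentence concludes that the sample size should therefore not constrain the primary analysis. No adjusted model, balance criterion or sensitivity analysis is specified. Descriptive summaries of patient characteristics and possible exploratory subgroup analyses are mentioned.

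**The concern.** Matching protects against confounding only by the factors that are matched, and here it is the only protection in the design. If a factor outside the list differs systematically between the prospective and historical patients and also affects the outcome, its effect is counted as an effect of the heated circuit. Neither the p-value nor the confidence interval allows for that.

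The plan's own background gives a reason to consider the bypass course: "Cooling and rewarming during CPB and takes considerable time and contributes to the post-procedural coagulopathy and physiologic perturbations". Coagulopathy is a secondary outcome, yet bypass exposure enters the matching only through deep hypothermic arrest and, indirectly, type of surgery.

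The two groups are also assembled differently. For prospective patients, "Informed consent will be obtained from next of kin / power of attorney"; no such step is described for historical controls. If a surrogate is harder to reach for urgent or night-time cases, those cases would be thinned out in the treated group only. That is a possible route to systematic imbalance, not a demonstrated one.

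At stake is whether a difference in time to normothermia, extubation time or coagulation values can be attributed to the heated circuit. Bias could create an apparent benefit or hide a real one.

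**Working it through.** **Inputs from the plan** (Data Analysis & Statistical Considerations): "a study of 14 prospectively enrolled patients and 28 retrospectively matched patients"; SD 1.3 h; target difference 1.25 h; alpha 0.05, with sidedness not stated. The documents give no covariate effects and no imbalances, so those are assumed below and shown as ranges.

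**1. The plan's own figure.** It says the study "would attain 82% power to detect a 1.25 hour difference".
- Standard error = 1.3 × √(1/14 + 1/28) = 1.3 × 0.3273 = 0.4255 h.
- Noncentrality = 1.25 / 0.4255 = 2.94, with 40 degrees of freedom and two-sided critical value 2.021.
- Power = 81.8%, which reproduces the stated 82%. The sample size figure is not in error.
- Smallest significant difference at the planned SD = 2.021 × 0.4255 = 0.86 h.

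**2. Bias from one uncontrolled factor (assumed values).** Let r be the factor's within-group correlation with time to normothermia after matching, and SMD its systematic standardised difference between groups. Then bias = r × SMD × 1.3 h. The false-positive rate is the chance that the two-sided t-test rejects when the circuit has no effect, with noncentrality = bias / 0.4255.

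| r | SMD | Bias (h) | Share of 1.25 h | False-positive rate |
|---|---|---|---|---|
| 0.2 | 0.25 | 0.07 | 5% | 5.3% |
| 0.3 | 0.5 | 0.20 | 16% | 7.3% |
| 0.4 | 0.5 | 0.26 | 21% | 9.2% |
| 0.5 | 0.5 | 0.33 | 26% | 11.6% |

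These are per factor. Several factors could add up or cancel.

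**3. What adjustment costs.** Four covariates at one degree of freedom each leave 36. Residual variance is multiplied by (1 − R²), where R² is the share of outcome variance that the covariates explain. The variance of the treatment estimate is multiplied by a variance inflation factor (VIF) if the covariates differ between groups.
- Balanced (VIF 1): power is 81.6% at R² = 0, 85.4% at 0.1 and 89.2% at 0.2.
- Four mutually uncorrelated covariates, each imbalanced by 0.5 SD: VIF = 1 + [14 × 28 / (42 × 40)] × (4 × 0.5²) = 1 + 0.233 × 1 = 1.23. Power is about 73% at R² = 0, 77–78% at 0.1 and 82% at 0.2.

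**4. Why a balance threshold should not select covariates.** A covariate with no systematic difference still has a chance SMD with SD √(1/14 + 1/28) = 0.327. It exceeds 0.25 in absolute value with probability 2 × [1 − Φ(0.25/0.327)] = 0.445, so a rule of adjusting above 0.25 would pick up about 45% of balanced covariates.

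**The case against.** The strongest reply has four parts.

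*The text is softer than a ban.* Adjustment is only not expected to be needed, and the matching list is introduced as what the criteria ought to include, so it is not declared complete. Type of surgery and deep hypothermic arrest may carry part of the bypass course. Descriptive tables could reveal an imbalance. All of this stands as a limit on the claim. It does not supply control: no adjusted analysis is specified, and an open-ended list is weak support for saying that the key confounders are matched.

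*Nothing shows that confounding is present.* A reader might infer that the primary result will be confounded by these four factors. The documents do not support that. The background links bypass cooling and rewarming to coagulopathy and physiologic disturbance, not to rewarming time in the ICU. It never links age, sex or urgency to rewarming. No enrolment hours or emergency case mix are given, so the surrogate-consent route is conjecture. This part stands in full.

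*Small groups are not evidence of bias.* With 14 against 28, a standardised difference of up to about 0.64 (1.96 × 0.327) is unremarkable by chance. That imbalance is already reflected in the standard error. Only a systematic difference supports the bias argument, so this too stands.

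*Adjustment is not free.* A reader might infer that it would simply raise power to 85–89%. That holds only if the covariates are balanced and informative. Under the imbalance that makes adjustment worthwhile, power may fall or stay level. This is correct, but imbalance is also where the unadjusted comparison is least reliable.

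**Conclusion.** The concern holds in a limited form. The stated reason for not adjusting does not cover bypass duration, age, sex or urgency. Following the plan as written leaves these uncontrolled in a comparison with historical controls. Confounding by them cannot be excluded, and its size and direction are unknown.

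The figures of 0.07 to 0.33 h and 5.3% to 11.6% illustrate one factor under assumed correlations and imbalances, a linear effect and the planned SD. They are not estimates for this study. At the mild end the effect is negligible. At the other end it is about a quarter of the target difference. The stated power is unaffected.

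This is a should-fix: the gap is real and cheap to close, but the documents do not establish that the result would be materially biased.

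**What to change.** Delete the sentence saying that no further adjustment is expected to be necessary. Before outcomes are examined:

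- Pre-specify one small regression of time to normothermia on treatment group with a fixed covariate list: bypass duration, age, sex, and elective or urgent status. All four are settled before ICU warming starts and should be available in the chart.
- Use the same list for the numeric secondary outcomes.
- Report the adjusted result alongside the unadjusted comparison, and state in advance which one carries the conclusion.
- Report standardised differences for baseline variables descriptively, without using a cut-off such as 0.25 to choose covariates.
- State whether the matching list is complete.

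The cost is a few chart fields per patient, some wording in the analysis section and about 4 of 40 degrees of freedom. If the covariates turn out to be imbalanced, the interval will be wider, as the power range in the working shows. The plan should acknowledge that price.
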